7.5 Study size

This is a non-interventional study which plans to enroll a minimum of 40 patients. No formal sample size calculation based on the primary endpoint of long-term safety is performed.

Protocols for observational studies (or registry studies) to assess the natural history of a disease or to evaluate the safety of an established product (investigational drug) may not include formal sample size calculations. Data on global epidemiology of NTDT are scarce, see Section 7.2. Also the prevalence of NTDT patients with clinically significant iron overload constitutes a very small percentage of total number of NTDT patients.

Given the small prevalence of the disease under consideration, data on the 40 patients would provide relevant data as described by the computation of probabilities to detect adverse events as shown below. Statistical computations were performed (see table below) to evaluate probabilities to detect at least one patient with an AE given 40 patients and different scenarios of AE incidence rates (Hanley and Lippman-Hand 1983). This table shows a reasonable chance to detect adverse events occurring with an incidence of 5% or higher.

Probability to observe at least one AE for different incidence rates:

Incidence rate of an adverse event	Probability that at least one patient out of 40 experiences the adverse event
3%	0.70
4%	0.80
5%	0.87
6%	0.92
10%	0.99

Incidence rate of an adverse event	Probability that at least one patient out of 40 experiences the adverse event
15%	1.00

7.6 **Data management**

Data will be entered routinely into the study database by the physician/study coordinator.

Novartis personnel (or designated CRO) will review the data entered by investigational staff for completeness and accuracy.

Page 44

Electronic data queries stating the nature of the problem and requesting clarification will be created for all other discrepancies and missing values and sent to the investigational site via the EDC system. Designated physician site staff is required to respond promptly to queries and to make any necessary changes to the data.

Concomitant treatments entered into the database will be coded using the WHO Drug Reference List, which employs the Anatomical Therapeutic Chemical classification system. Medical history/current medical conditions, cause of death and adverse events will be coded using the Medical dictionary for regulatory activities (MedDRA) terminology.

At the conclusion of the study, the occurrence of any protocol violations will be determined. After this action has been completed and the database has been declared to be complete and accurate, it will be locked and made available for data analysis. Any changes to the database after that time can only be made by joint written agreement between the Global Head of Data Management, Therapeutic Area Head, Biostatistics Development Unit Head.

7.7 Data analysis

This is a non-interventional pediatric study that does not impose a therapy protocol, diagnostic/therapeutic interventions or a visit schedule. Data will be collected on all eligible pediatric patients aged ≥ 10 to <18 years at enrollment with non-transfusion dependent thalassemia treated with deferasirox and will be followed for up to 5 years from the start of deferasirox treatment. Retrospective data collection will be done for patients who have started deferasirox 12 months or less prior to enrollment.

The baseline is defined as the timeframe before the patient starts treatment with deferasirox.

Post baseline data will be collected from the start date of deferasirox and then on for five years.

The data will be analyzed by Novartis and/or a designated CRO.

Continuous variables will be summarized by number of patients, mean, standard deviation, minimum, 25th-percentile, median, 75th percentile and maximum. Categorical variables will be summarized by absolute and relative frequencies.

In addition to the statistical methods outlined below, further details and any additional, exploratory analyses that may be performed will be described in the Statistical Analysis Plan (SAP).

7.7.1 **Analysis sets**

7.7.1.1 **Full Analysis Set**

The Full Analysis Set (FAS) comprises all patients who received at least one dose of deferasirox during the study.

7.7.1.2 Safety Set

The Safety Set includes all patients who received at least one dose of deferasirox during the study and have at least one post-baseline safety assessment. For post-baseline safety assessments, if a patient has any assessment taken a day after treatment start date for examination based assessments, e.g. laboratory, the patient will be included. For AE/ Death patients with an AE start date/ death date on or after the start date of treatment will be considered as having as least one post-baseline safety assessment and will be included in the safety set.

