7.7.4.1 Variable

The primary variable is the proportion of patients having SAEs that are considered to be related to study drug over the period of up to 5 years from the start of deferasirox treatment.

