7.7.4.2 Statistical hypothesis, model, and method of analysis

Counts and frequencies of patients with any drug related SAEs will be provided descriptively on Safety Set overall and by preferred term and system organ class.

In case of high number of SAEs, exposure-adjusted adverse event incidence will also be tabulated.

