The occurrence of adverse events should be sought by non-directive questioning of the patient at each visit during the study. All adverse event reported by the patients will be recorded in the case report form. Adverse events also may be detected when they are volunteered by the patient during or between visits or through physical examination, laboratory test, or other assessments.

All adverse events must be recorded on the Adverse Events case report/case record form (eCRF) with the following information:

- the severity grade (mild, moderate, or severe)
- its relationship to the drug(s) of interest (suspected/not suspected)

- its duration (start and end dates or if continuing at final exam)
- whether it constitutes a serious adverse event (SAE)
- action taken with respect to study or investigational treatment (none, dose adjusted, temporarily interrupted, permanently discontinued
- whether medication or therapy was given (no concomitant medication/non-drug therapy, concomitant medication/non-drug therapy)

The start and end dates of deferasirox treatment is recorded on the Dose Administration Record eCRF. Any change, interruption or discontinuation of dose requires assessment of attribution to an adverse event.

Any adverse event which is fatal is recorded as a serious adverse event with attribution listing the cause of death, as per the Serious Adverse Event eCRF.

Unlike routine safety assessments, SAEs are monitored continuously and have special reporting requirements, as stated below.

Laboratory test abnormalities

Abnormal laboratory values or test results that constitute adverse events or underlying conditions should not be reported separately in addition to the respective adverse events or underlying diagnosis.

Additionally, laboratory abnormalities that are considered clinically significant due to induction of clinical signs or symptoms, or requiring concomitant therapy (e.g. any hematologic abnormality that requires transfusion or cytokine treatment) or changes in study medication(s), should be recorded on the Adverse Events eCRF. Whenever possible, a diagnosis, rather than a symptom should be provided (e.g. anemia instead of low hemoglobin). Laboratory abnormalities that meet the criteria for Adverse events should be followed until they have returned to normal or an adequate explanation of the abnormality is found.

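### Safety Set membership in 7.7.1.2 partly depends on the outcome: an adverse event admits a treated patient, but no stated route admits one whose adverse-event enquiry was negative and who has no post-baseline examination

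*Protocol*

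**What the plan says.** The Safety Set (Protocol 7.7.1.2) consists of patients who "received at least one dose of deferasirox during the study and have at least one post-baseline safety assessment". The section then says how that condition is met:

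- By examination: "if a patient has any assessment taken a day after treatment start date for examination based assessments, e.g. laboratory, the patient will be included".
- By event: "For AE/ Death patients with an AE start date/ death date on or after the start date of treatment will be considered" to have had at least one such assessment.

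The endpoint is fixed in 7.7.4.1: "The primary variable is the proportion of patients having SAEs that are considered to be related to study drug". The denominator follows in 7.7.4.2: "Counts and frequencies of patients with any drug related SAEs will be provided descriptively on Safety Set". Section 7.7.6 puts the other safety tables on the same set, and 7.7.3 does so for exposure.

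A set without the post-baseline condition already exists in 7.7.1.1: "The Full Analysis Set (FAS) comprises all patients who received at least one dose of deferasirox during the study". It is used for baseline and efficacy summaries, not for the primary endpoint.

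Two other places bear on what counts as an assessment. Section 9 says: "The occurrence of adverse events should be sought by non-directive questioning of the patient at each visit during the study". In Table 7-2, footnote 4 marks the rows regarded as safety assessments. Physical examination, height, weight, vital signs and most laboratory rows carry it; the Adverse Events row does not.

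**The concern.** Consider two treated children, neither with a recorded examination after the start date. One reports an adverse event and enters the Safety Set. The other is asked, reports nothing, and has no stated way in. The event is what separates them, so membership of the denominator depends in part on the outcome being counted.

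Timing is asymmetric in the same direction: an adverse event on the start date itself counts, while an examination has to come after that date.

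Every treated patient with a drug-related SAE is always in the set, because the SAE is itself an adverse event. Patients can be lost only from among those with no adverse event. If any are lost, the primary proportion and the incidences in the AE tables can move only upward, and they no longer describe all treated children.

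**Working it through.** **The plan's own figures.** Section 7.5 tabulates the chance of seeing at least one patient with an adverse event among 40, which is 1−(1−p)^40. For p = 3, 4, 5, 6, 10 and 15% this gives 0.704, 0.805, 0.871, 0.916, 0.985 and 0.998, against the printed 0.70, 0.80, 0.87, 0.92, 0.99 and 1.00. The table reproduces. It takes all 40 patients as evaluable.

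**Inputs.**

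- N = 40, the planned minimum (7.5).
- e = number of patients with a drug-related SAE. I take e = 2 as an illustration.
- k = treated patients with no adverse event, no death and no post-baseline examination. The protocol gives no value, so the range 0 to 8 is my assumption.

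**Counts.** On all treated patients the proportion is e/N. On the Safety Set as worded it is e/(N−k), since all e stay in and only event-free patients leave. The ratio N/(N−k) does not depend on e and is never below 1.

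| k | e/(N−k) with e = 2 | N/(N−k) |
|---|---|---|
| 0 | 2/40 = 5.00% | 1.000 |
| 1 | 2/39 = 5.13% | 1.026 |
| 2 | 2/38 = 5.26% | 1.053 |
| 4 | 2/36 = 5.56% | 1.111 |
| 8 | 2/32 = 6.25% | 1.250 |

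A relative change above 10% needs k = 4, since 40/37 = 1.081 and 40/36 = 1.111.

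**In expectation.** Let π be the SAE probability, q the probability of any adverse event (q ≥ π), and m the probability of having no post-baseline examination, taken as independent of events. A treated patient is excluded with probability m(1−q), so the expected proportion is about π/(1−m(1−q)). With π = 5% and m = 10%, both assumed:

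- q = 5%: 0.05/(1−0.10×0.95) = 5.52%
- q = 50%: 0.05/(1−0.10×0.50) = 5.26%
- q = 80%: 0.05/(1−0.10×0.20) = 5.10%

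Any adverse event admits a patient, not only a drug-related SAE. The effect therefore shrinks as adverse events of any kind become common.

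**Exposure-adjusted rates.** Exposure is summarised on the Safety Set, so the patient-years of excluded event-free patients are lost too. These rates can also move only upward, by an amount that depends on those patients' time on drug.

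**The case against.** The strongest case against is that the excluded patient hardly exists. Any one weight, vital sign, physical examination or laboratory value after the start date is enough. Table 7-2 suggests these at each visit, and Section 9 places the adverse-event questioning at those same visits. Dosing is by body weight, and 7.1 recommends weekly creatinine checks in the first month and monthly ones later. Section 7.4 commits to capturing whatever the chart holds. This stands, and it is why k is probably small. It does not guarantee k = 0, because no visit schedule is imposed and laboratory data are collected only when available.

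Second, the exclusion is partly inferred. Section 7.7.1.2 gives two sufficient conditions and never says that a negative enquiry fails to count. Section 7.3 lists adverse events among the data by which safety is monitored, and the SAP, which may say more, is not at hand. This also stands in part. Still, the protocol states the routes in, and Amendment 4 records that the criteria were added to clarify membership. An SAP that follows the protocol closely would inherit the gap between them.

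Third, the AE/death clause is protective: without it, a child with an early SAE and no later examination would drop out of the numerator. That is right, and the clause should stay.

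Fourth, a patient with neither an examination nor an adverse-event record may have had no follow-up at all. Counting that patient as event-free can understate risk. That is a good reason not to make the all-treated proportion the only one shown.

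A reader might infer that the primary proportion is in fact biased upward, or that the children lost would mainly be early leavers. The documents support neither. They give no k above zero and say nothing about who would lack an examination.

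**Conclusion.** The point holds as a wording defect with a known direction and an unknown, probably small, size. As written, only treated patients without an adverse event can be left out of the Safety Set, so any distortion of the primary proportion is upward. At N = 40 it is a factor of 1.03 for one excluded patient and 1.05 for two; with none excluded it is nil.

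For scale, one excluded patient moves 2/40 from 5.0% to 5.1%, while the exact 95% interval for 2/40 runs from about 0.6% to 17%. The analysis is descriptive, and no test or decision threshold depends on it.

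The conclusion rests on reading the two stated routes as the full list, which the missing footnote on the Adverse Events row supports and the list in 7.3 weakens. It also treats excluded patients who were asked and reported nothing as true non-cases. This is a minor point, worth making because the repair is so cheap.

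**What to change.** In 7.7.1.2, add a sentence stating that a post-baseline contact at which adverse events were sought and none was reported counts as a post-baseline safety assessment. Keep the AE/death clause as it is, and bring the Adverse Events row of Table 7-2 into line by giving it footnote 4.

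In the report, give the number of treated patients with no post-baseline information, and show the primary proportion on all treated patients (FAS) beside the Safety Set result.

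The cost is a sentence, a footnote mark and one extra line of output, with no new assessments. The small downside is that the all-treated proportion counts patients without any follow-up as non-cases; the reported number lets the reader judge how much that matters. If k turns out to be zero, the two proportions coincide and nothing is lost.

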7.7.2 Patient demographics/other baseline characteristics

Demographics and other baseline data and disease characteristics will be summarized descriptively using the FAS.

7.7.3 Treatments (study treatment, concomitant therapies, compliance)

Using the Safety Set, data on deferasirox dose and exposure (duration of exposure, total patientyears exposure, reason for dose increase or decrease, average dose, number of interruptions and reason) and concomitant therapies will be summarized descriptively.

Primary objective 7.7.4

The primary objective is to evaluate the long term safety of deferasirox as determined by adverse events.

7.7.4.1 Variable

The primary variable is the proportion of patients having SAEs that are considered to be related to study drug over the period of up to 5 years from the start of deferasirox treatment.

7.7.4.2 Statistical hypothesis, model, and method of analysis

Counts and frequencies of patients with any drug related SAEs will be provided descriptively on Safety Set overall and by preferred term and system organ class.

In case of high number of SAEs, exposure-adjusted adverse event incidence will also be tabulated.

7.7.4.3 Handling of missing values/censoring/discontinuations

Details on imputation of missing data will be described in the SAP.

7.7.5 Secondary objectives

To evaluate the incidence of serum creatinine and ALT increases in 7.7.5.1 actual practice setting

Counts and frequencies will be provided on Safety Set for patients with:

- Serum creatinine > 33 % above baseline and the age adjusted ULN (as per local normal ranges) in at least two consecutive post-baseline measurements at least 7 days apart from each other:
- SGPT (ALT) above 5 x ULN in at least two consecutive post-baseline measurements at least 7 days apart from each other.

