Both adults and pediatric population (21 patients) under 18 years were included in the efficacy and safety analysis. Diarrhea, rash and nausea were the most frequent study drug-related AEs. Both diarrhea and rash were more frequent in the 10 mg/kg/day deferasirox, group than in the 5 mg/kg/day deferasirox group or the placebo groups, but no difference between groups was observed for nausea. There were no deaths, and the incidence of SAEs was comparable between treatment groups. Eight patients experienced AEs resulting in study discontinuation (Taher A, et. al., Blood 2012).

Renal function, assessed by measuring serum creatinine, creatinine clearance and Urinary Protein Creatinine Ratio (UPCR), was only mildly affected by deferasirox, which was reflected by a small number of patients developing abnormal values, that resolved spontaneously or after drug interruption. There were no progressive changes in mean serum creatinine, creatinine clearance, or UPCR.

Both ALT and AST parameters were decreased slightly over time in patients on deferasirox and these were more evident in the higher dose group. Shifts from below ULN at baseline to above ULN occurred in about a third of the patients with normal baseline values, and there were no relevant differences between deferasirox- and placebo-treated patients. No patients receiving deferasirox demonstrated an increase in ALT >5 x ULN and >2x baseline, although this did occur in one patient on placebo 10mg/kg/day.

The safety profile over 2 years of deferasirox treatment did not differ from that observed in the core 1-year study (Taher A, et. al., poster 3258; ASH 2012). Moreover, findings from subanalysis of the THALASSA study confirm that the safety profile of deferasirox remains consistent as patients with NTDT approach the lower iron burden of LIC <3 mg Fe/g dw. The exposure-adjusted AE incidence in the patients not achieving LIC<3 did not differ from those reaching LIC<3. Increases in serum creatinine observed in three patients (>33% increase from

baseline and >ULN on two consecutive occasions) receiving deferasirox, treatment were reversible on dose interruption. These results suggest that the target of LIC <3 mg Fe/g dw may be reached with appropriate deferasirox treatment without increased risk of over chelation (Taher A, et. al., poster 391, EHA 2013).

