Non-interventional study (NIS)' in this context is used synonymously with 'observational study', i.e., does not involve any kind of intervention, experimental or otherwise. In these studies, interviews, questionnaires and blood samples may be performed as normal clinical practice.

6 Research question and objectives

This observational study will evaluate the long term safety of deferasirox therapy in pediatric patients ≥ 10 to ≤ 18 years at enrollment with NTDT in actual practice setting.

Table 6-1 Objectives and Endpoints

Objectives	Endpoints	Analysis
Primary		
Evaluate the long term safety of deferasirox	Proportion of patients having SAEs that are considered to be related to study drug up to 5 years from the start of deferasirox treatment	Section 7.7.4
Secondary		

Evaluate the incidence of serum creatinine and SGPT (ALT) increases in actual practice setting	The proportion of patients having (up to 5 years from the start of deferasirox treatment): Serum creatinine > 33 % above baseline and above the age adjusted ULN in at least two consecutive post-baseline measurements at least 7 days apart from each other. SGPT (ALT) above 5 x ULN in at least two consecutive post-baseline measurements at least 7 days apart from each other	Section 7.7.5.1
Evaluate renal and hepatic safety parameters over time	Absolute/relative changes from baseline of SGPT (ALT), SGOT (AST), total bilirubin, alkaline phosphatase, serum creatinine, creatinine clearance quarterly up to 5 years. Proportion of patients having hepatic and renal clinical events that are considered to be related to study drug up to 5 years from the start of deferasirox.	Section 7.7.5.2
Evaluate growth by gender	Absolute change in BMI, weight and height from baseline to EOS Proportion of patients falling behind in growth based on height, weight and BMI	Section 7.7.5.3
Evaluate sexual development by gender	Mean age at assessment for each Tanner stage Changes from baseline to the last on-study value of all Tanner stage parameters.	Section 7.7.5.4
Evaluate long term efficacy of deferasirox as measured by serum ferritin and LIC	Absolute/relative change in SF and LIC from baseline to EOS Proportion of patient achieving a SF <300 ng/mL Proportion of patients achieving LIC <3 mg Fe/g dw Proportion of patients reinitiating deferasirox after discontinuation due to a "stopping rule" *	Section 7.7.5.5

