In NTDT, a combination of increased intestinal iron over-absorption and occasional transfusions results in an iron accumulation rate which is much slower than in patients with transfusion dependent thalassemias. As a result, patients with NTDT tend to present with some degree of iron overload later in their life compared to transfusion dependent patients. This fact limits the pool of patients who could potentially meet the eligibility criteria and be enrolled in to the study. Furthermore, the feasibility which was conducted in major thalassemia countries

confirmed the limited number of pediatric patients with NTDT who can be treated with deferasirox.

Patients will be enrolled if they meet the following criteria.

Inclusion criteria:

Patients eligible for inclusion in this study must meet all of the following criteria:

1. Male or female aged \geq 10 but <18 years old with non-transfusion-dependent thalassemia syndromes inclusive of beta-thalassemia intermedia, HbE beta-thalassemia or alpha thalassemia intermedia (HbH disease) and chronic iron overload

AND

2. Patients currently treated for a maximum of 12 months or patients planned to be treated with deferasirox

AND

3. Written informed consent obtained prior to any screening procedures. The consent form will be signed by the patient's legal guardian.

Exclusion Criteria

1. Patients treated with deferasirox in an interventional clinical study.

7.3 **Variables**

Treatment

Treating the Patient

The study being non-interventional, the patient will be treated at the physician's discretion and according to the local country-specific deferasirox prescribing information.

The starting dose of deferasirox, subsequent dose adjustments and treatment interruption will be at the physician's discretion and according to the local country-specific prescribing information and will be recorded on the Dosage Administration Record eCRF together with the reasons for the dose changes and interruptions.

Drug Compliance

The compliance will be assessed by caregiver interviews. The caregiver will be asked how many doses, if any, of deferasirox treatment was missed in the last treatment period.

Drug Accountability

Not applicable since commercial drug is used.

IWR (Interactive Web Response System)

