7.7.6.3 Laboratory abnormalities

All laboratory values will be converted into SI units and the severity grade calculated using the low/normal/high classifications based on laboratory normal ranges and for selected parameters by notable/extended ranges (see Table 7-3 below).

The following summaries will be generated separately for hematology, biochemistry and urinary laboratory tests:

- shift tables using normal/notable/extended ranges to compare baseline to the worst ontreatment value.
- listing of all laboratory data with values flagged to show the corresponding normal/notable/extended ranges.

For each hematology/iron metabolism parameter, observed values (and changes from baseline) will be summarized by descriptive statistics (n, mean, standard deviation, minimum, lower quartile, median, upper quartile and maximum).

Creatinine clearance estimated using the Schwarz formula for patients < 18 years old and Cockcroft-Gault formula for patients ≥ 18 years old will be displayed using relative change from baseline by categories.

Similar to adverse events, the number of events related to lab abnormalities adjusted by time of exposure (events per year or events per month) will be tabulated.

Table 7-3	Criteria for clinically	notable and extended	laboratory ranges
1 abic 1 -5	Officeria for Chilicany	, iiotabie alia extellaca	iaboratory ranges

Parameter	Criteria
ALT/AST	>5×ULN and >2×baseline value (extended range >10×ULN and >2×baseline value)
Serum creatinine	>33% increase from baseline and >ULN at two consecutive measurements at least 7 days apart
Creatinine clearance	<60 mL/min at two consecutive measurements at least 7 days apart (extended range <40 mL/min)

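### The ALT endpoint for the increases objective has no baseline term, so a patient already above 5 x ULN who stays above it is counted as an on-treatment increase

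*Protocol*

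**What the plan says.** Table 6-1 lists as a secondary objective "Evaluate the incidence of serum creatinine and SGPT (ALT) increases in actual practice setting". For ALT, Table 6-1 and Section 7.7.5.1 give the same endpoint: the proportion of patients with "SGPT (ALT) above 5 x ULN in at least two consecutive post-baseline measurements at least 7 days apart from each other", over up to 5 years and on the Safety Set. The creatinine endpoint beside it in Table 6-1 is "Serum creatinine > 33 % above baseline and above the age adjusted ULN in at least two consecutive post-baseline measurements", so it requires both a rise over baseline and a level above normal.

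Section 7.7.6.3 defines notable ranges in Table 7-3. For ALT and AST the criterion is ">5×ULN and >2×baseline value (extended range >10×ULN and >2×baseline value", with no confirmation. For creatinine it is ">33% increase from baseline and >ULN at two consecutive measurements at least 7 days apart", which has the same baseline and confirmation terms as the secondary endpoint. Section 5 reports the earlier randomised study in this disease on the baseline-referenced ALT criterion: "No patients receiving deferasirox demonstrated an increase in ALT >5 x ULN and >2x baseline".

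Section 7.2 has one exclusion criterion: "Patients treated with deferasirox in an interventional clinical study". The inclusion criteria concern age, diagnosis with chronic iron overload, deferasirox use and consent. None limits ALT. Under Section 7.1 and Table 7-2, a baseline laboratory value is collected only if it was taken within 1.5 months before the first dose.

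**The concern.** The objective asks about a rise; the ALT rule measures a level. The two differ for any patient whose ALT is above 5 x ULN before the first dose. Such patients can enter: Section 5 describes iron accumulating mainly in hepatocytes with a risk of fibrosis and cirrhosis, and nothing in Section 7.2 screens on liver tests.

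The study is descriptive and has no concurrent comparator, so nothing in the design subtracts abnormality that was present at entry. A reader will take the ALT proportion as what happened on the drug. With about 40 patients, one misclassified patient is visible in the result.

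**Working it through.** **The rules side by side**

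- ALT, Table 6-1 and 7.7.5.1: above 5 x ULN, confirmed at least 7 days apart, no baseline term.
- ALT, Table 7-3: above 5 x ULN and above 2 x baseline, no confirmation.
- Creatinine, both places: more than 33% above baseline, above ULN, confirmed at least 7 days apart.

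Creatinine has a baseline term wherever it appears. ALT has one in Table 7-3 but not in the endpoint that serves the objective on increases.

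**Applying the ALT rules to illustrative courses**

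Values are in multiples of ULN and are assumed; measurements fall on days 14, 28 and 60. The last column counts only patients not above 5 x ULN at baseline and keeps the 7.7.5.1 confirmation.

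| Baseline | Post-baseline values | 7.7.5.1 | Table 7-3 | Baseline-restricted count |
|---|---|---|---|---|
| 6 | 6, 6, 6 | counted | no (needs > 2 x 6 = 12) | no |
| 6 | 5.8, 5.5, 5.2 | counted | no (needs > 12) | no |
| 3 | 5.5, 5.5, 4 | counted | no (5.5/3 = 1.83) | counted |
| 1 | 8, 4, 1 | no (not confirmed) | counted | no |
| 1 | 8, 8, 1 | counted | counted | counted |

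The first two rows are the problem: one patient is unchanged, the other improves, and both are reported as increases. Rows three and four show that 7.7.5.1 and Table 7-3 also part ways for other reasons, in both directions.

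**Size**

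The protocol has no figure for this endpoint. Its one calculation is the table in Section 7.5, the probability of at least one event among 40 patients. The formula 1 - (1 - p)^40 gives 0.704, 0.805, 0.872, 0.916, 0.985 and 0.999 at 3, 4, 5, 6, 10 and 15%, which agrees with the printed values.

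With a denominator of 40, each patient who stays above 5 x ULN from baseline adds 1/40 = 2.5 percentage points.

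The prevalence q of baseline ALT above 5 x ULN is not given, so it is assumed over a range. The expected number is 40q, and the chance of at least one is 1 - (1 - q)^40:

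| Assumed q | Expected of 40 | Chance of at least one |
|---|---|---|
| 1% | 0.4 | 0.33 |
| 2.5% | 1 | 0.64 |
| 5% | 2 | 0.87 |
| 10% | 4 | 0.99 |

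These figures concern entry above the limit. Being counted also requires two qualifying values after baseline, so they are upper limits for the miscount.

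**Do other planned outputs separate these patients?**

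Only partly. The summaries of change from baseline in 7.7.5.2 are by quarter and do not identify individuals. In the shift tables of 7.7.6.3, nobody can be notable for ALT at baseline, because no value exceeds twice itself. The stable patient at 6 x ULN therefore shows no shift to notable there, but is an increase in 7.7.5.1. The flagged listings would let a reader trace the case by hand.

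**The case against.** The strongest reply is that the protocol already plans both an absolute and a baseline-referenced ALT measure. Table 7-3 uses the same terms as the earlier study, and 7.7.6.3 plans shift tables, flagged listings and exposure-adjusted counts of laboratory abnormalities. An absolute threshold can also be applied when baseline ALT is missing, which is likely for some patients given the 1.5-month window and the retrospective entries. A rule requiring more than 2 x baseline would miss a rise from 4 to 7 x ULN (7/4 = 1.75).

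Much of this stands, and it shapes the fix: the absolute count should stay, and the 2 x baseline criterion should not replace it. It does not answer the central point. The endpoint assigned to the objective on increases still counts patients whose ALT did not increase.

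Some stronger readings are tempting, but the protocol does not support them:

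- A reader might infer that 7.7.5.1 and Table 7-3 contradict each other. They serve different outputs, and Table 6-1 and 7.7.5.1 agree on the endpoint. The two ALT rules are unreconciled, not contradictory.
- A reader might infer that the registry cannot be compared with the earlier study. Table 7-3 already gives a count on that study's criterion.
- A reader might infer that closely monitored patients are lost through the requirement for consecutive values at least 7 days apart. That needs a strict adjacent-pair reading and repeated rechecks under 7 days apart. The ALT checks recommended in Section 7.1 are every 2 weeks in the first month and then monthly, which does not produce it.
- A reader might make something of Table 7-3 omitting the age adjustment of the creatinine ULN. Section 7.7.5.1 ties that limit to local normal ranges, 7.7.6.3 also uses laboratory normal ranges, and no difference in counts is shown.

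**Conclusion.** The point holds in a limited form. As written, the ALT endpoint counts as an on-treatment increase any patient already above 5 x ULN at baseline whose confirmed post-baseline values remain above 5 x ULN, including one who is improving. This does not extend to pre-existing liver disease in general: a patient whose ALT stays at or below 5 x ULN never qualifies.

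Each affected patient adds 2.5 percentage points, assuming a Safety Set of exactly the planned minimum of 40. A reader might go on to infer a bias of several points, but the protocol gives no prevalence of baseline ALT above 5 x ULN, and Section 5 reports that ALT fell slightly over time on deferasirox in the earlier study. The number affected may be zero. The case for changing the rule is that it does not match its objective and costs little to correct, not that a known bias has been shown.

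**What to change.** In Table 6-1 and Section 7.7.5.1:

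1. Count as ALT increases only patients who were not already above 5 x ULN at baseline, with the confirmation rule unchanged.
2. Report separately the patients with baseline ALT above 5 x ULN and the patients with no baseline ALT, each with the number meeting the present rule.
3. Give alongside this the number meeting the Table 7-3 criterion, so that the two ALT counts can be read together.
4. Keep the present absolute count as supplementary.

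The cost is a change of wording in two places, minor programming on data already collected, and one or two extra table rows. The denominator shrinks slightly: with one patient above the limit at baseline it is 39, and a single case becomes 1/39 = 2.6% instead of 2.5%. A true further rise in a patient who started above 5 x ULN leaves the main count. It remains in the separate row, and also appears under Table 7-3 if it exceeds twice the baseline value.
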